9.10. Other aspects

Not applicable.

10. PROTECTION OF HUMAN SUBJECTS

10.1. Patient information

All parties will comply with all applicable laws, including laws regarding the implementation of organizational and technical measures to ensure protection of patient personal data. Such measures will include omitting patient names or other directly identifiable data in any reports, publications, or other disclosures, except where required by applicable laws.

Patient personal data will be stored by Optum in encrypted electronic form and will be password protected to ensure that only authorized study staff have access. Optum will implement appropriate technical and organizational measures to ensure that the personal data can be recovered in the event of disaster. In the event of a potential personal data breach, Optum shall be responsible for determining whether a personal data breach has in fact occurred and, if so, providing breach notifications as required by law.

To protect the rights and freedoms of natural persons with regard to the processing of personal data, when study data are compiled for transfer to Pfizer and other authorized parties, any patient names will be removed and will be replaced by a single, specific, numerical code. All other identifiable data transferred to Pfizer or other authorized parties will be identified by this single, patient-specific code. In case of data transfer, Pfizer will maintain high standards of confidentiality and protection of patients' personal data consistent with the clinical study agreement and applicable privacy laws. There is no planned transfer of study data under this study protocol.

10.2. Patient consent

As this study does not involve data subject to privacy laws according to applicable legal requirements, obtaining informed consent from patients by Pfizer is not required.

10.3. Institutional review board (IRB)

There must be prospective approval of the study protocol, protocol amendments, and other relevant documents from the relevant IRBs. All correspondence with the IRB/independent ethics committee must be retained. Copies of IRB approvals must be forwarded to Pfizer.

Optum will prepare and submit the appropriate documents to a relevant IRB. Optum will communicate directly with the IRB to address any questions and/or provide any additional information in connection with the reviews. The IRB will monitor the study for the life of the project and may require formal re-review and approval on an annual basis. Changes to the project may also require re-review and approval by the IRB.

10.4. Ethical conduct of the study

The study will be conducted in accordance with legal and regulatory requirements, as well as with scientific purpose, value, and rigor and follow generally accepted research practices described in Guidelines for GPP issued by the International Society for Pharmacoepidemiology (ISPE), and the European Medicines Agency, ENCePP Guide on Methodological Standards in Pharmacoepidemiology.

The conduct and reporting of this study follow Optum Epidemiology's SOPs that are consistent with the ISPE's GPP (ISPE 2015).

11. MANAGEMENT AND REPORTING OF ADVERSE EVENTS/ADVERSE REACTIONS

This study does not involve medical record review by the treating physician. External physician adjudicators will review medical records to confirm select outcomes among a subset of patients, as described in Section 9.3.1.3.

11.1. Structured data analysis

This study involves data that exist as structured data by the time of study start. In these data sources, it is not possible to link (ie, identify a potential association between) a particular product and medical event for any individual. Thus, the minimum criteria for reporting an adverse event (AE) (ie, identifiable patient, identifiable reporter, a suspect product, and event) cannot be met.

11.2. Human review of unstructured data

This study protocol requires human review of patient-level unstructured data; unstructured data refer to verbatim medical data, including text-based descriptions and visual depictions of medical information, such as medical records, images of physician notes, neurological scans, x-rays, or narrative fields in a database. The reviewer is obligated to report AEs with explicit attribution to any Pfizer drug that appear in the reviewed information (defined per the patient population and study period specified in the protocol). Explicit attribution is not inferred by a temporal relationship between drug administration and an AE but must be based on a definite statement of causality by a healthcare provider linking drug administration to the AE.

The requirements for reporting safety events on the non-interventional study (NIS) adverse event monitoring (AEM) Report Form to Pfizer Safety are as follows:

- All serious and non-serious AEs with explicit attribution to any Pfizer drug that appear
 in the reviewed information must be recorded on the data collection tool and reported,
 within 1 business day of awareness of the study team, to Pfizer Safety using the NIS
 AEM Report Form.
- Scenarios involving drug exposure, including exposure during pregnancy, exposure during breast feeding, medication error, overdose, misuse, extravasation, lack of efficacy, and occupational exposure associated with the use of a Pfizer product must be reported, within 1 business day of awareness, to Pfizer Safety using the NIS AEM Report Form.
- For exposure during pregnancy in studies of pregnant women, data on the exposure to PAXLOVID during pregnancy, are not reportable unless associated with serious or nonserious adverse events.
- For these AEs with an explicit attribution or scenarios involving exposure to a Pfizer product, the safety information identified in the unstructured data reviewed is captured in the Event Narrative section of the report form, and constitutes all clinical information known regarding these AEs. No follow-up on related AEs will be conducted.

All the demographic fields on the NIS AEM Report Form may not necessarily be completed, as the form designates, since not all elements will be available due to privacy concerns with the use of secondary data sources. While not all demographic fields will be completed, at the very least, at least 1 patient identifier (eg, gender, age as captured in the narrative field of the form) will be reported on the NIS AEM Report Form, thus allowing the report to be considered a valid one in accordance with pharmacovigilance legislation. All identifiers will be limited to generalities, such as the statement "A 35-year-old female..." or "An elderly male..." Other identifiers will have been removed.

Additionally, the onset/start dates and stop dates for "Illness," "Study Drug," and "Drug Name" may be documented in month/year (mmm/yyyy) format rather than identifying the actual date of occurrence within the month /year of occurrence in the day/month/year (DD/MMM/YYYY) format.

All research staff members involved in the review of medical charts and completion of the NIS AEM Report Form must complete the following Pfizer training requirements:

• "Your Reporting Responsibilities (YRR) Training for Vendors."

These trainings must be completed by research staff members prior to the start of unstructured data collection. All trainings include a "Confirmation of Training Certificate" (for signature by the trainee) as a record of completion of the training, which must be kept in a retrievable format. Copies of all signed training certificates must be provided to Pfizer.

Re-training must be completed on an annual basis using the most current YRR training materials.

12. PLANS FOR DISSEMINATING AND COMMUNICATING STUDY RESULTS

The final study report will be posted on the HMA-EMA Catalogues of RWD Studies. Manuscripts based on specific outcomes of interest may be developed for publication purposes.

In the event of any prohibition or restriction imposed (eg, clinical hold) by an applicable competent authority in any area of the world, or if Optum becomes aware of any new information which might influence the evaluation of the benefits and risks of a Pfizer product, Pfizer should be informed immediately.

ANNEX 1. LIST OF STAND ALONE DOCUMENTS

None

ANNEX 2. ADDITIONAL INFORMATION

Teratogenic drugs used for exclusion

Teratogenic Drugs	Half-life Range	Reference(s)
angiotensin-converting- enzyme (ACE) inhibitors	<1 to 17 hours	Sanders et al. 2011
angiotensin II receptor blocker*	2 to 24 hours	Burnier 2001
carbamazepine	18 to 65 hours	Bertilsson 1978
chemotherapeutic drugs for the treatment of cancer	Variable (maximum: 215 hours [mitoxantrone])	Ehninger et al. 1986
dolutegravir	14 hours	Mulligan et al. 2018
fluconazole	20 to 50 hours	Brammer et al. 1990
isotretinoin	Up to 29 hours	Brazzell et al. 1982
lithium	Up to 3 days following continuous therapy	Goodnick et al. 1981
methotrexate	Up to 69 hours	Shen et al. 1978
methylene blue	Up to 24 hours	Peter et al. 2000
misoprostol	<1 hour	Davies et al. 2001
mitoxantrone	215 hours	Ehninger et al. 1986
mycophenolate	Up to 17 hours	Fulton et al. 1996
penicillamine	Up to 6 days following treatment cessation	Munro et al. 1997
phenobarbital	Up to 132 hours	Nelson et al. 1982
phenytoin	Up to 42 hours	Ahn et al. 2008
teriflunomide	18 to 19 days	FDA 2012
thalidomide	<8 hours	Teo et al. 2004
topiramate	Up to 56 hours	FDA 1996
valproic acid	10 to 16 hours	Gugler et al. 1980
warfarin	Up to 40 hours	Walfisch et al. 2010

^{*} Exposure in 2nd or 3rd trimester

Codes for the identification of pregnancy and infant outcomes

All codes are ICD-10 diagnosis codes unless otherwise specified.

Pregnancy Outcomes

The pregnancy outcomes to be assessed are:

- SA
 - O02.1 Missed abortion

- O03.0 Genital tract and pelvic infection following incomplete spontaneous abortion
- O03.1 Delayed or excessive hemorrhage following incomplete spontaneous abortion
- O03.2 Embolism following incomplete spontaneous abortion
- O03.30 Unspecified complication following incomplete spontaneous abortion
- O03.31 Shock following incomplete spontaneous abortion
- O03.32 Renal failure following incomplete spontaneous abortion
- O03.33 Metabolic disorder following incomplete spontaneous abortion
- O03.34 Damage to pelvic organs following incomplete spontaneous abortion
- O03.35 Other venous complications following incomplete spontaneous abortion
- O03.36 Cardiac arrest following incomplete spontaneous abortion
- O03.37 Sepsis following incomplete spontaneous abortion
- O03.38 Urinary tract infection following incomplete spontaneous abortion
- O03.39 Incomplete spontaneous abortion with other complications
- O03.4 Incomplete spontaneous abortion without complication
- O03.5 Genital tract and pelvic infection following complete or unspecified spontaneous abortion
- O03.6 Delayed or excessive hemorrhage following complete or unspecified spontaneous abortion
- O03.7 Embolism following complete or unspecified spontaneous abortion
- O03.80 Unspecified complication following complete or unspecified spontaneous abortion
- O03.81 Shock following complete or unspecified spontaneous abortion
- O03.82 Renal failure following complete or unspecified spontaneous abortion
- O03.83 Metabolic disorder following complete or unspecified spontaneous abortion
- O03.84 Damage to pelvic organs following complete or unspecified spontaneous abortion
- O03.85 Other venous complications following complete or unspecified spontaneous abortion

- O03.86 Cardiac arrest following complete or unspecified spontaneous abortion
- O03.87 Sepsis following complete or unspecified spontaneous abortion
- O03.88 Urinary tract infection following complete or unspecified spontaneous abortion
- O03.89 Complete or unspecified spontaneous abortion with other complications
- O03.9 Complete or unspecified spontaneous abortion without complication
- O31.1--- Continuing pregnancy after spontaneous abortion of 1 fetus or more
- O31.2--- Continuing pregnancy after intrauterine death of 1 fetus or more
- O36.4--- Maternal care for intrauterine death
- CPT 59800⁴ Treatment of spontaneous abortion, first trimester
- CPT 59801 Treatment of spontaneous abortion, first trimester
- CPT 59810 Treatment of spontaneous abortion, second trimester
- CPT 59811 Treatment of spontaneous abortion, second trimester
- CPT 59812 Treatment of incomplete abortion, any trimester, completed surgically
- CPT 59820 Treatment of missed abortion, completed surgically; first trimester
- CPT 59821 Treatment of missed abortion, completed surgically; second trimester

Induced termination

- O04.5 Genitl tret and pelvic infet fol (induced) term of pregnancy
- O04.6 Delayed or excess hemor fol (induced) term of pregnancy
- O04.7 Embolism following (induced) termination of pregnancy
- O04.80 (Induced) termination of pregnancy with unsp complications
- O04.81 Shock following (induced) termination of pregnancy
- O04.82 Renal failure following (induced) termination of pregnancy

⁴ CPT copyright 2022 American Medical Association. All rights reserved.

Fee schedules, relative value units, conversion factors and/or related components are not assigned by the AMA, are not part of CPT, and the AMA is not recommending their use. The AMA does not directly or indirectly practice medicine or dispense medical services. The AMA assumes no liability for data contained or not contained herein.

CPT is a registered trademark of the American Medical Association.

- O04.83 Metabolic disorder following (induced) term of pregnancy
- O04.84 Damage to pelvic organs fol (induced) term of pregnancy
- O04.85 Oth venous comp following (induced) termination of pregnancy
- O04.86 Cardiac arrest following (induced) termination of pregnancy
- O04.87 Sepsis following (induced) termination of pregnancy
- O04.88 Urinary tract infection fol (induced) term of pregnancy
- O04.89 (Induced) termination of pregnancy with other complications
- O07.0 Genitl tret and pelvic infet fol failed attempt term of preg
- O07.1 Delayed or excess hemor fol failed attempt term of pregnancy
- O07.2 Embolism following failed attempted termination of pregnancy
- O07.30 Failed attempted termination of pregnancy w unsp comp
- O07.31 Shock following failed attempted termination of pregnancy
- O07.32 Renal failure following failed attempted term of pregnancy
- O07.33 Metabolic disorder fol failed attempt term of pregnancy
- O07.34 Damage to pelvic organs fol failed attempt term of pregnancy
- O07.35 Oth venous comp following failed attempted term of pregnancy
- O07.36 Cardiac arrest following failed attempted term of pregnancy
- O07.37 Sepsis following failed attempted termination of pregnancy
- O07.38 Urinary tract infection fol failed attempt term of pregnancy
- O07.39 Failed attempted termination of pregnancy w oth comp
- O07.4 Failed attempted termination of pregnancy w/o complication
- Z33.2 Encounter for elective termination of pregnancy
- ICD-10 Procedure 10A00ZZ Abortion of Products of Conception, Open Approach
- ICD-10 Procedure 10A03ZZ Abortion of Products of Conception, Percutaneous Approach
- ICD-10 Procedure 10A04ZZ Abortion of Products of Conception, Perc Endo Approach
- ICD-10 Procedure 10A07Z6 Abortion of Products of Conception, Vacuum, Via Opening
- ICD-10 Procedure 10A07ZW Abortion of Products of Conception, Laminaria, Via Opening

- ICD-10 Procedure 10A07ZX Abortion of POC, Abortifacient, Via Opening
- ICD-10 Procedure 10A07ZZ Abortion of Products of Conception, Via Opening
- ICD-10 Procedure 10A08ZZ Abortion of Products of Conception, Endo
- HCPCS S0190 Mifepristone ORAL 200 mg
- HCPCS S0191 Misoprostal oral 200 mcg
- HCPCS S0199 Medically induced abortion by oral ingestion of medication including all associated services and supplies
- HCPCS S2260 Induced abortion, 17-24 weeks
- HCPCS S2262 Abortion for maternal indication, 25 weeks or greater
- HCPCS S2265 Induced abortion, 25-28 weeks
- HCPCS S2266 Induced abortion, 29-31 weeks
- HCPCS S2267 Induced abortion, 32 weeks/greater
- CPT 01964⁵ Anesthesia for abortion procedures
- CPT 01965 Anesthesia for incomplete or missed abortion procedures
- CPT 01966 Anesthesia for induced abortion procedures
- CPT 59840 Induced abortion, by dilation and curettage
- CPT 59841 Induced abortion, by dilation and evacuation
- CPT 59850 Induced abortion, by 1 or more intra-amniotic injections (amniocentesis-injections), including hospital admission and visits, delivery of fetus and secundines;
- CPT 59851 Induced abortion, by 1 or more intra-amniotic injections (amniocentesis-injections), including hospital admission and visits, delivery of fetus and secundines; with dilation and curettage and/or evacuation
- CPT 59852 Induced abortion, by 1 or more intra-amniotic injections (amniocentesis-injections), including hospital admission and visits, delivery of fetus and secundines; with hysterotomy (failed intra-amniotic injection)
- CPT 59855 Induced abortion, by 1 or more vaginal suppositories (eg, prostaglandin) with or without cervical dilation (eg, laminaria), including hospital admission and visits, delivery of fetus and secundines;
- CPT 59856⁶ Induced abortion, by 1 or more vaginal suppositories (eg, prostaglandin) with or without cervical dilation (eg, laminaria), including

⁵ CPT copyright 2022 American Medical Association. All rights reserved.

⁶ CPT copyright 2022 American Medical Association (AMA). All rights reserved.

hospital admission and visits, delivery of fetus and secundines; with dilation and curettage and/or evacuation

CPT 59857 Induced abortion, by 1 or more vaginal suppositories (eg, prostaglandin) with or without cervical dilation (eg, laminaria), including hospital admission and visits, delivery of fetus and secundines; with hysterotomy (failed medical evacuation)

Stillbirth

- O31.2--- Continuing pregnancy after intrauterine death of 1 fetus or more
- O36.4--- Maternal care for intrauterine death
- P95 Stillbirth
- Z37.1 Single stillbirth
- Z37.3 Twins, 1 liveborn and 1 stillborn
- Z37.4 Twins, both stillborn
- Z37.60 to Z37.64, Z37.69 Multiple births, some liveborn
- Z37.7 Other multiple births, all stillborn

• Livebirth

- Z37.0 Single livebirth
- Z37.2 Twins, both liveborn
- Z37.50 Multiple births, unspecified, all liveborn
- Z37.51 Triplets, all liveborn
- Z37.52 Quadruplets, all liveborn
- Z37.53 Quintuplets, all liveborn
- Z37.54 Sextuplets, all liveborn
- Z37.59 Other multiple births, all liveborn
- Z38.00 Single liveborn infant, delivered vaginally
- Z38.01 Single liveborn infant, delivered by cesarean
- Z38.1 Single liveborn infant, born outside hospital
- Z38.2 Single liveborn infant, unspecified as to place of birth
- Z38.30 Twin liveborn infant, delivered vaginally
- Z38.31 Twin liveborn infant, delivered by cesarean
- Z38.4 Twin liveborn infant, born outside hospital

- Z38.5 Twin liveborn infant, unspecified as to place of birth
- Z38.61 Triplet liveborn infant, delivered vaginally
- Z38.62 Triplet liveborn infant, delivered by cesarean
- Z38.63 Quadruplet liveborn infant, delivered vaginally
- Z38.64 Quadruplet liveborn infant, delivered by cesarean
- Z38.65 Quintuplet liveborn infant, delivered vaginally
- Z38.66 Quintuplet liveborn infant, delivered by cesarean
- Z38.68 Other multiple liveborn infant, delivered vaginally
- Z38.69 Other multiple liveborn infant, delivered by cesarean
- Z38.7 Other multiple liveborn infant, born outside hospital
- Z38.8 Other multiple liveborn infant, unsp as to place of birth

The following livebirth codes are used to identify livebirths in multiple gestation pregnancies with more than 1 outcome type:

- Z37.3 Twins, 1 liveborn and 1 stillborn
- Z37.60 Multiple births, unspecified, some liveborn
- Z37.61 Triplets, some liveborn
- Z37.62 Quadruplets, some liveborn
- Z37.63 Quintuplets, some liveborn
- Z37.64 Sextuplets, some liveborn
- Z37.69 Other multiple births, some liveborn

Infant Outcomes

The infant outcomes to be assessed are:

- Preterm birth
 - O60.1 Preterm labor with preterm delivery
 - P07.2 Extreme immaturity of newborn
 - P07.3 Preterm [premature] newborn [other]
 - P07.30 Preterm newborn, unspecified weeks of gestation
 - P07.31 Preterm newborn, gestational age 28 completed weeks
 - P07.32 Preterm newborn, gestational age 29 completed weeks
 - P07.33 Preterm newborn, gestational age 30 completed weeks
 - P07.34 Preterm newborn, gestational age 31 completed weeks
 PFIZER CONFIDENTIAL

- P07.35 Preterm newborn, gestational age 32 completed weeks

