9.3.1.1. Pregnancy outcomes

The pregnancy outcomes to be assessed are:

- SA defined as the loss of pregnancy before the 20th week of gestation
- Induced termination defined as an intervention to end a pregnancy so that it does not result in a livebirth
- Stillbirth defined as the loss of pregnancy at or after the 20th week of gestation
- Livebirth a delivered fetus with any sign of life (eg, voluntary movement, heartbeat) regardless of gestational weeks

Lists of ICD-10 diagnostic codes are provided in ANNEX 2. ADDITIONAL INFORMATION.

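### Annex 2 lists codes for continuing pregnancies, failed terminations and missed-abortion anaesthesia as pregnancy losses or terminations, against the definitions in Section 9.3.1.1

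*Protocol*

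**What the plan says.** Section 9.3.1.1 sets the definitions at the level of the pregnancy:

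- "SA defined as the loss of pregnancy before the 20th week of gestation"
- "Stillbirth defined as the loss of pregnancy at or after the 20th week of gestation"
- "Induced termination defined as an intervention to end a pregnancy so that it does not result in a livebirth"

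The section refers to Annex 2 for the codes. Table 4 (Section 9.7.2.2) gives the pregnancy as the unit of analysis for all three outcomes.

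Annex 2 contains these entries:

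- SA list: O31.1, "Continuing pregnancy after spontaneous abortion of 1 fetus or more", and O31.2, "Continuing pregnancy after intrauterine death of 1 fetus or more".
- Stillbirth list: O31.2 again.
- Induced termination list: O07.0 to O07.4, ending with "Failed attempted termination of pregnancy w/o complication".
- Induced termination list: CPT 01965, "Anesthesia for incomplete or missed abortion procedures".

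Section 9.3.1 sends potential induced terminations to medical record adjudication but does not name SA or stillbirth. Section 9.3.1.3 handles those two through published claims algorithms, with positive predictive values of 84.7% for SA and 83% for stillbirth.

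**The concern.** The labels of these codes describe something other than the outcome under which they are filed. A pregnancy that continues has not been lost. A failed attempt has not ended the pregnancy. Anaesthesia for a missed or incomplete abortion belongs with the treatment of a spontaneous loss.

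The consequences differ by outcome. For SA and stillbirth, a wrongly flagged pregnancy goes through with no record check and can enter the primary comparison. For induced termination, the wrong flags mainly affect the interim tabulations and the claims-based analyses, and they add candidates to a record review that is capped at 550 requests for all outcomes.

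**Working it through.** No figure in the protocol depends on these codes, so the check sets the lists against the definitions and then follows each code to the analysis it reaches.

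**1. Labels against definitions**

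| Code | Listed under | What the label describes | Fits Section 9.3.1.1? |
|---|---|---|---|
| O31.1 | SA | one or more fetuses lost, pregnancy goes on | No, the pregnancy is not lost |
| O31.2 | SA and stillbirth | one or more fetuses die in utero, pregnancy goes on | No, the pregnancy is not lost |
| O07.0–O07.4 | induced termination | an attempt that failed | No, the label does not show that the pregnancy ended |
| CPT 01965 | induced termination | anaesthesia for incomplete or missed abortion | No, the matching codes (O02.1, CPT 59812, 59820, 59821) are in the SA list |

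**2. Two cases run through the lists as written**

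- A twin pregnancy loses one fetus at week 9 and delivers a live infant at term. O31.1 meets the SA list and the delivery code meets the livebirth list. The same pregnancy with a fetal death after week 20 meets the stillbirth list through O31.2.
- A missed abortion is treated surgically under anaesthesia. CPT 59820 meets the SA list and CPT 01965 meets the induced termination list.

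**3. Where each error can be caught**

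- SA and stillbirth: there is no adjudication (Sections 9.3.1 and 9.3.1.3). Section 9.7.2.3 admits events found by a published validated algorithm to the primary comparison without confirmation. Section 9.7.1 says claims definitions are deliberately sensitive, but only for outcomes that will be validated by record review, so that reasoning does not cover these two.
- Induced termination: potential cases are adjudicated, and Section 9.7.2.3 limits the primary comparison to confirmed or validated-algorithm events. A false flag should be removed there. It remains in the interim tabulations and the claims-based analyses. Section 9.3.1.3 puts record eligibility at about 50% and retrieval at 70% to 85%, so the reach of review is 0.50 × 0.70 = 35% to 0.50 × 0.85 = 42.5%.

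**4. Possible size for SA and stillbirth (assumed inputs)**

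The protocol does not say how often these codes occur. Suppose a share f of comparator events is false, and false events are equally common in both cohorts. A true relative risk of 2.0 is then observed as 2(1 − f) + f = 2 − f:

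- f = 1%: 1.99
- f = 5%: 1.95
- f = 10%: 1.90

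For scale, if all the error implied by the quoted predictive values is treated this way, f = 1 − 0.847 = 15.3% gives 1.85 for SA, and f = 1 − 0.83 = 17% gives 1.83 for stillbirth. These two values reflect all sources of false positives, not the O31 codes alone.

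**The case against.** The strongest reply is that a code list is not a decision rule. Section 9.2.3 says pregnancy outcome and end date come from a set of algorithms applied to such codes, and a precedence rule for conflicting codes may sit there or in the SAP. That is fair, and it is why a reader who infers that three outcomes are in fact misclassified goes further than the protocol supports. What stands is that Annex 2, as the stated list, includes codes that contradict the definitions and gives no restriction on their use.

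Second, mixed-outcome multiple pregnancies are foreseen. The stillbirth list includes Z37.3 and the Z37.6 codes, and Annex 2 adds livebirth codes for pregnancies with more than one outcome type. Section 9.7.2 will describe multiple gestations and may restrict some sensitivity analyses to singletons. Capturing partial loss may therefore be deliberate. However, the Annex 2 note concerns livebirth codes only, the singleton restriction is optional, and Section 9.3.1.1 still speaks of loss of the pregnancy.

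Third, the published SA and stillbirth algorithms already acknowledge false positives through their predictive values, and deleting codes could depart from the validated version. The protocol does not show whether those algorithms contain O31.1 or O31.2, so the fix has to allow for both cases.

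Fourth, induced termination is largely protected. Cases are adjudicated, claims profiles are screened before records are requested, and Section 9.7.1 warns that interim counts will be too high. This stands for the primary comparison and weakens any claim that many record requests would be wasted.

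Finally, a reader might treat O36.4, or O31.2, as an error simply because it appears under both SA and stillbirth. It is not: the week-20 boundary in Section 9.3.1.1 separates the two outcomes. The fault with O31.2 is that its label describes a pregnancy that continues.

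**Conclusion.** The contradiction between the Annex 2 labels and the Section 9.3.1.1 definitions is certain. It matters most for SA and stillbirth, where a multifetal pregnancy with a partial loss and a livebirth can be counted as an event and no record review would remove it. For induced termination the effect should be confined to the interim tabulations and the claims-based analyses.

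The size is unknown. The protocol gives no frequencies for these codes, so no percentage inflation of SA or of terminations can be derived from it. If false events are equally common in both cohorts and make up 1% to 10% of comparator events, the distortion of a relative risk of 2.0 is modest (1.99 to 1.90). Nothing in the protocol indicates that the error differs between cohorts. The conclusion assumes that the lists are applied as written, and an unseen precedence rule could reduce the effect or remove it.

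**What to change.** Change Annex 2 as follows:

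1. Do not let O31.1 or O31.2 alone define SA or stillbirth. Use them to flag fetal loss in a multiple gestation, and set the pregnancy outcome from the later end-of-pregnancy code. If the validated published algorithms include these codes, say so and report results with and without them.
2. Count O07.x as induced termination only when a completed-termination code is also present and no livebirth follows.
3. Move CPT 01965 to the SA list as a supporting code.

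Deal with SA and stillbirth first, since they have no adjudication to fall back on. The cost is a code-list edit and reprogramming. The downside is small: a few true terminations coded only as O07.x or CPT 01965 would be missed.
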